17.3.1.1.2. Non-Measurable

All other lesions, including small lesions (longest diameter < 10 mm or pathological lymph nodes with ≥ 10 to < 15 mm short axis), as well as truly non-measurable lesions. Lesions considered truly non-measurable include: leptomeningeal disease, ascites, pleural or pericardial effusion, inflammatory breast disease, lymphangitic involvement of skin or lung, and abdominal masses/abdominal organomegaly identified by physical exam that is not measurable by reproducible imaging techniques.

17.3.1.1.3. Special Considerations Regarding Lesion Measurability

Bone lesions, cystic lesions, and lesions previously treated with local therapy require particular comment.

17.3.1.1.3.1. Bone Lesions

- Bone scan, positron emission tomography (PET) scan or plain films are not considered adequate imaging techniques to measure bone lesions. However, these techniques can be used to confirm the presence or disappearance of bone lesions.
- Lytic bone lesions or mixed lytic-blastic lesions, with identifiable soft tissue components, that can be evaluated by cross-sectional imaging techniques such as CT

or MRI can be considered as measurable lesions if the soft tissue component meets the definition of measurability described above.

- Blastic bone lesions are non-measurable.

17.3.1.1.3.2. Cystic Lesions

- Lesions that meet the criteria for radiographically defined simple cysts should not be considered as malignant lesions (neither measurable nor non-measurable) since they are, by definition, simple cysts.
- “Cystic lesions” thought to represent cystic metastases can be considered as measurable lesions, if they meet the definition of measurability described above. However, if noncystic lesions are present in the same subject, these are preferred for selection as target lesions.

17.3.1.1.3.3. Lesions with Prior Local Treatment

- Tumor lesions situated in a previously irradiated area, or in an area subjected to other loco-regional therapy, are not considered measurable unless there has been demonstrated progression in the lesion.

17.3.1.2. Specifications by Methods of Measurements

17.3.1.2.1. Measurement of Lesions

All measurements should be recorded in metric notation, using calipers if clinically assessed. All baseline evaluations should be performed as close as possible to the treatment start and NEVER more than 28 days before randomization/registration.

17.3.1.2.2. Method of Assessment

The same method of assessment and the same technique should be used to characterize each identified and reported lesion at baseline and during follow-up. Imaging based evaluation should always be performed rather than clinical examination unless the lesion(s) being followed cannot be imaged but are assessable by clinical exam.

CT, MRI: CT is the best currently available and reproducible method to measure lesions selected for response assessment. This guideline has defined measurability of lesions on CT scan based on the assumption that CT slice thickness is 5 mm or less. When CT scans have slice thickness greater than 5 mm, the minimum size for a measurable lesion should be twice the slice thickness. MRI is also acceptable in certain situations (eg, for body scans).

17.3.2. Tumor Response Evaluation

17.3.2.1. Assessment of Overall Tumor Burden and Measurable Disease

To assess objective response or future progression, it is necessary to estimate the overall tumor burden at baseline and use this as a comparator for subsequent measurements.

In this study, only subjects with measurable disease at baseline should be included.

17.3.2.2. Baseline Documentation of “Target” and “Non-target” Lesions

When more than 1 measurable lesion is present at baseline, all lesions up to a maximum of 5 lesions total (representative of all involved organs) should be identified as target lesions and will be recorded and measured at baseline (this means in instances where subjects have only 1 or 2 organ sites involved a maximum of 2 and 4 lesions respectively will be recorded).

Target lesions should be selected on the basis of their size (lesions with the longest diameter), be representative of all involved organs, but in addition should be those that lend themselves to reproducible repeated measurements. It may be the case that, on occasion, the largest lesion does not lend itself to reproducible measurement in which circumstance the next largest lesion which can be measured reproducibly should be selected.

Lymph nodes merit special mention since they are normal anatomical structures which may be visible by imaging even if not involved by tumor. As noted above, pathological nodes which are defined as measurable and may be identified as target lesions must meet the criterion of a short axis of ≥ 15 mm by CT scan. Only the short axis of these nodes will contribute to the baseline sum. The short axis of the node is the diameter normally used by radiologists to judge if a node is involved by solid tumor. Nodal size is normally reported as 2 dimensions in the plane in which the image is obtained (for CT scan this is almost always the axial plane; for MRI the plane of acquisition may be axial, sagittal, or coronal). The smaller of these measures is the short axis. For example, an abdominal node which is reported as being 20 mm \times 30 mm has a short axis of 20 mm and qualifies as a malignant, measurable node. In this example, 20 mm should be recorded as the node measurement. All other pathological nodes (those with short axis ≥ 10 mm but < 15 mm) should be considered non-target lesions. Nodes that have a short axis < 10 mm are considered non-pathological and should not be recorded or followed.

A sum of the diameters (longest for non-nodal lesions, short axis for nodal lesions) for all target lesions will be calculated and reported as the baseline sum diameters. If lymph nodes are to be included in the sum, then as noted above, only the short axis is added into the sum. The baseline sum diameters will be used as reference to further characterize any objective tumor regression in the measurable dimension of the disease.

All other lesions (or sites of disease) including pathological lymph nodes should be identified as non-target lesions and should also be recorded at baseline. Measurements are not required and these lesions should be followed as “present,” “absent,” or in rare cases “unequivocal progression.” In addition, it is possible to record multiple non-target lesions involving the same organ as a single item on the case record form (eg, “multiple enlarged pelvic lymph nodes” or “multiple liver metastases”).

17.3.2.3. Response Criteria

This section provides the definitions of the criteria used to determine objective tumor response for target lesions.

17.3.2.3.1. Evaluation of Target Lesions

CR: Disappearance of all target lesions. Any pathological lymph nodes (whether target or non-target) must have reduction in short axis to < 10 mm.

PR: At least a 30% decrease in the sum of diameters of target lesions, taking as reference the baseline sum diameters.

PD: At least a 20% increase in the sum of diameters of target lesions, taking as reference the smallest sum on study (this includes the baseline sum if that is the smallest on study). In addition to the relative increase of 20%, the sum must also demonstrate an absolute increase of at least 5 mm. (Note: the appearance of 1 or more new lesions is also considered progression).

SD: Neither sufficient shrinkage to qualify for PR nor sufficient increase to qualify for PD, taking as reference the smallest sum diameters while on study.

17.3.2.3.2. Special Notes on the Assessment of Target Lesions

Lymph nodes: Lymph nodes identified as target lesions should always have the actual short axis measurement recorded (measured in the same anatomical plane as the baseline examination), even if the nodes regress to below 10 mm on study. This means that when lymph nodes are included as target lesions, the “sum” of lesions may not be zero even if CR criteria are met, since a normal lymph node is defined as having a short axis of < 10 mm. For PR, SD, and PD, the actual short axis measurement of the nodes is to be included in the sum of target lesions.

Target lesions that become “too small to measure”: While on study, all lesions (nodal and non-nodal) recorded at baseline should have their actual measurements recorded at each subsequent evaluation, even when very small (eg, 2 mm). However, sometimes lesions or lymph nodes which are recorded as target lesions at baseline become so faint on CT scan that the radiologist may not feel comfortable assigning an exact measure and may report them as being “too small to measure.” When this occurs, it is important that a value be recorded on the eCRF. If it is the opinion of the radiologist that the lesion has likely disappeared, the measurement should be recorded as 0 mm. If the lesion is believed to be present and is faintly seen but too small to measure, a default value of 5 mm should be assigned. (Note: It is less likely that this rule will be used for lymph nodes since they usually have a definable size when normal and are frequently surrounded by fat such as in the retroperitoneum; however, if a lymph node is believed to be present and is faintly seen but too small to measure, a default value of 5 mm should be assigned in this circumstance as well). This default value is derived from the 5 mm CT slice thickness (but should not be changed with varying CT slice thickness). The measurement of these lesions is potentially non-reproducible, therefore providing this default value will prevent false responses or progressions based upon measurement error. To reiterate, however, if the radiologist is able to provide an actual measure, that should be recorded, even if it is below 5 mm.

Lesions that split or coalesce on treatment: When non-nodal lesions “fragment,” the longest diameters of the fragmented portions should be added together to calculate the target lesion sum. Similarly, as lesions coalesce, a plane between them may be maintained that would aid in obtaining maximal diameter measurements of each individual lesion. If the lesions have truly coalesced such that they are no longer separable, the vector of the longest diameter in this instance should be the maximal longest diameter for the “coalesced lesion.”

17.3.2.3.3. Evaluation of Non-target Lesions

This section provides the definitions of the criteria used to determine the tumor response for the group of non-target lesions. While some non-target lesions may actually be measurable, they

need not be measured and instead should be assessed only qualitatively at the time points specified in the protocol.

CR: Disappearance of all non-target lesions and normalization of tumor marker level. All lymph nodes must be non-pathological in size (< 10 mm short axis).

Non-CR/Non-PD: Persistence of 1 or more non-target lesion(s) and/or maintenance of tumor marker level above the normal limits.

PD: Unequivocal progression (see comments below) of existing non-target lesions (Note: the appearance of 1 or more new lesions is also considered progression).

17.3.2.3.4. Special Notes on Assessment of Progression of Non-target Disease

The concept of progression of non-target disease requires additional explanation as follows:

When the subject also has measurable disease: In this setting, to achieve “unequivocal progression” on the basis of the non-target disease, there must be an overall level of substantial worsening in non-target disease such that, even in presence of SD or PR in target disease, the overall tumor burden has increased sufficiently to merit discontinuation of therapy. A modest “increase” in the size of 1 or more non-target lesions is usually not sufficient to qualify for unequivocal progression status. The designation of overall progression solely on the basis of change in non-target disease in the face of SD or PR of target disease will therefore be extremely rare.

When the subject has only non-measurable disease: The same general concepts apply here as noted above, however, in this instance there is no measurable disease assessment to factor into the interpretation of an increase in non-measurable disease burden. Because worsening in non-target disease cannot be easily quantified (by definition: if all lesions are truly non-measurable) a useful test that can be applied when assessing subjects for unequivocal progression is to consider if the increase in overall disease burden based on the change in non-measurable disease is comparable in magnitude to the increase that would be required to declare PD for measurable disease (ie, an increase in tumor burden representing an additional 73% increase in ‘volume’ [which is equivalent to a 20% increase diameter in a measurable lesion]). If ‘unequivocal progression’ is seen, the subject should be considered to have had overall PD at that point. While it would be ideal to have objective criteria to apply to non-measurable disease, the very nature of that disease makes it impossible to do so, therefore the increase must be substantial.

17.3.2.3.5. New Lesions

The appearance of new malignant lesions denotes disease progression; therefore, some comments on detection of new lesions are important. There are no specific criteria for the identification of new radiographic lesions; however, the finding of a new lesion should be unequivocal: ie, not attributable to differences in scanning technique, change in imaging modality or findings thought to represent something other than tumor (for example, some “new” bone lesions may be simply healing or flare of preexisting lesions). This is particularly important when the subject’s baseline lesions show PR or CR. For example, necrosis of a liver lesion may be reported on a CT scan report as a “new” cystic lesion, which it is not.

A lesion identified on a follow-up study in an anatomical location that was not scanned at baseline is considered a new lesion and will indicate disease progression. An example of this is

the subject who has visceral disease at baseline and while on study has a CT or MRI brain ordered which reveals metastases. The subject’s brain metastases are considered to be evidence of PD even if he/she did not have brain imaging at baseline.

If a new lesion is equivocal, for example because of its small size, continued therapy and follow-up evaluation will clarify if it represents truly new disease. If repeat scans confirm there is definitely a new lesion, then progression should be declared using the date of the initial scan.

17.3.2.4. Evaluation of Best Overall Response

The best overall response is the best response recorded from the start of the study treatment until the EOT. Confirmatory measurement for CR, PR, or SD is required in the study.

The subject’s best overall response assignment will depend on the findings of both target and non-target disease and will also take into consideration the appearance of new lesions.

17.3.2.4.1. Time Point Response

It is assumed that at each protocol-specified time point, a response assessment occurs. [Table 17.2](#) provides a summary of the overall response status calculation at each time point for subjects who have measurable disease at baseline.

When subjects have non-measurable (therefore non-target) disease only, see [Table 17.2](#).

Table 17.2: Overall Response: Subjects with Target (+/-Non-target) Disease

Target lesions	Non-target lesions	New lesions	Overall response
CR	CR	No	CR
CR	Non-CR/non-PD	No	PR
CR	Not evaluated	No	PR
PR	Non-PD or not all evaluated	No	PR
SD	Non-PD or not all evaluated	No	SD
Not all Evaluated	Non-PD	No	NE
PD	Any	Yes or No	PD
Any	PD	Yes or No	PD
Any	Any	Yes	PD

CR = complete response, PR = partial response, SD = stable disease, PD = progressive disease, and NE = in-evaluable.

17.3.2.4.2. Missing Assessments and Inevaluable Designation

When no imaging/measurement is performed at all at a particular timepoint, the subject is not evaluable (NE) at that timepoint. If only a subset of lesion measurements are made at an assessment, usually the case is also considered NE at that timepoint, unless a convincing argument can be made that the contribution of the individual missing lesion(s) would not change the assigned time point response. This would be most likely to happen in the case of PD. For example, if a subject had a baseline sum of 50 mm with 3 measured lesions and at follow-up

only 2 lesions were assessed, but those gave a sum of 80 mm, the subject will have achieved PD status, regardless of the contribution of the missing lesion.

17.3.2.4.3. Best Overall Response: All Time Points

The best overall response is determined once all the data for the subject is known.

Best response determination in this study requires confirmation of CR or PR: Best response is defined as the lesser of the two best responses across 2 consecutive scans (eg, a subject who has PR at first assessment, SD at second assessment, and PD on last assessment; this would report as a best overall response of SD). When SD is believed to be best response, it must also meet the protocol specified minimum time from baseline, 6 weeks (± 7 days). If the minimum time is not met when SD is otherwise the best time point response, the subject's best response depends on the subsequent assessments. For example, a subject who has SD at first assessment, PD at second and does not meet minimum duration for SD, will have a best response of PD. The same subject lost to follow-up after the first SD assessment would be considered inevaluable.

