6.4.2. Every 6 Weeks (\pm 7 days)

- Record concomitant medications and AEs at every visit.
- Tumor assessments, based on sites of disease identified at Screening and any additional newly suspected sites of progressive disease, will be conducted every 6 weeks (\pm 7 days) from Cycle 1 Day 1, independent of treatment cycle. CT or MRI scans of the suspected sites of disease in the chest, abdomen and pelvis are mandatory. Computerized tomography and/or MRI (spiral CT or MRI with \leq 5 mm cuts) of chest, abdomen, and pelvis should be used for tumor assessment unless another modality of disease assessment is necessary for the lesions. The same assessment modality should be used throughout the study for all assessments for each subject unless prior approval is obtained from Sponsor or its designee. Unscheduled tumor assessments may be performed if progression is suspected.
- A CT or MRI of the brain is mandatory for all subjects included with baseline stable brain metastases. Subjects without brain metastases do not need additional brain scans for tumor assessment unless clinically indicated.

Imaging results will be reviewed by an independent radiologic facility.

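### The best-response rule can score PR-then-PD below SD-then-PD, sets no minimum interval for confirming a response, and does not say how an NE between two PRs is handled

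*Combined protocol and SAP*

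**What the plan says.** Section 17.3.2.4.3 opens its rule with "Best response determination in this study requires confirmation of CR or PR" and defines it as "Best response is defined as the lesser of the two best responses across 2 consecutive scans". Its one worked example is PR, then SD, then PD, scored SD.

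For SD the same paragraph uses time: "When SD is believed to be best response, it must also meet the protocol specified minimum time from baseline, 6 weeks", with a 7-day tolerance. A subject with SD at the first assessment who shows "PD at second and does not meet minimum duration for SD, will have a best response of PD".

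Section 17.3.2.4 says something different: "Confirmatory measurement for CR, PR, or SD is required in the study".

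On missing data, Section 17.3.2.4.2 makes a time point NE when no imaging is done, and adds: "If only a subset of lesion measurements are made at an assessment, usually the case is also considered NE at that timepoint". No section ranks NE against the other classes or says whether an NE time point is one of the two consecutive scans.

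On timing, Sections 6.4.2 and 17.3.2.5 schedule scans every 6 weeks, plus or minus 7 days. Section 6.4.2 adds: "Unscheduled tumor assessments may be performed if progression is suspected". Section 6.5 waives the end-of-treatment scan if the last one was within 6 weeks, but does not forbid it. Section 11.4.1.1 requires confirmation of CR and PR for the primary analysis and gives no interval.

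**The concern.** Best overall response determines the primary ORR (Section 11.4.1.1) and the secondary DCR, clinical benefit rate (CBR) and investigator-assessed ORR (Section 11.4.1.2.2). The pair rule is the only working definition of confirmation in the text, and its single example does not settle three situations:

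- a first PR followed directly by PD;
- two PR readings a short time apart;
- two PR readings separated by an NE.

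In the first, a tumor that shrank can be classed below one that did not. In the other two, a subject can be counted as a confirmed responder, or not, for reasons unrelated to the drug. Two programmers following the text could derive different responder counts from the same readings.

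**Working it through.** **The plan's own figures.** Section 11.6 takes n = 150 and an expected ORR of 35%. The smallest count whose exact 95% lower bound exceeds 20% is 41 (lower bound 20.4%).

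- P(X ≥ 41 | 150, 0.35) = 0.9816, against 98.2% stated.
- 30% of 150 is 45, and P(X ≥ 45 | 150, 0.35) = 0.9159, against 91.6% stated.

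Both reproduce and are not in dispute. One subject is 1/150 = 0.67 points.

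**Timing inputs.** Counting from Cycle 1 Day 1, the week-6 window is days 35 to 49 and the week-12 window is days 77 to 91. The shortest gap between two in-window scheduled scans is 77 − 49 = 28 days.

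**Sequences scored under the text.** In the third column, NE counts as a scan and ranks lowest.

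| Sequence (days) | Pair rule plus SD time rule (17.3.2.4.3) | Pair rule with SD also confirmed (17.3.2.4) | NE skipped |
|---|---|---|---|
| PR 42, SD 84, PD 126 (the protocol's example) | SD | SD | SD |
| PR 42, PD 84 | PD | PD | PD |
| SD 42, PD 84 | SD | PD | SD |
| PR 42, NE 84, PR 126, PD 168 | PD if NE counts as a scan | PD if NE counts as a scan | PR |
| PR 42, PR 84, NE 126, PD 168 | PR | PR | PR |
| PR 42, NE 84, PR 126, PR 168 | PR | PR | PR |
| PR 42, unscheduled PR 55, PD 84 | PR | PR | PR |

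**PR then PD.** The only pair is PR and PD, and the lesser is PD. For SD then PD, the paragraph assigns PD because the minimum time is not met. That condition has a purpose only if SD stands when the time is met. The ordering anomaly therefore exists within Section 17.3.2.4.3. If Section 17.3.2.4 governs, both sequences are PD and the time condition has no function here. ORR does not move, because a single PR followed by PD is unconfirmed on any rule. CBR does not move either, because PD at week 12 cannot follow more than 6 months of SD. Only DCR can move.

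**Short interval.** Day 55 lies outside both scheduled windows, so it is not part of the week-6 time point. It is 55 − 42 = 13 days after the first PR. The two readings are consecutive scans and both are PR, so the rule confirms a response that the next scheduled scan would not have confirmed.

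**NE between two PRs.** If NE is a scan result ranking below PR, neither pair containing it confirms PR. If NE is passed over, the two PRs are consecutive and the response stands. The outcome is undefined only when NE separates two isolated PRs.

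**Sensitivity of the plan's criteria (assumed rates, n = 150, ORR 35%).**

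| Assumption | Scored ORR | P(lower bound > 20%) | P(ORR ≥ 30%) |
|---|---|---|---|
| None affected | 35.0% | 98.2% | 91.6% |
| 2% of responders lost | 0.35 × 0.98 = 34.3% | 97.2% | 88.5% |
| 5% of responders lost | 0.35 × 0.95 = 33.25% | 95.0% | 82.4% |
| 1 point added by early confirmation | 36.0% | 99.0% | 94.9% |
| 2 points added by early confirmation | 37.0% | 99.5% | 97.0% |

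With 0.35 × 150 = 52.5 expected responders, the loss rows correspond to about 1.1 and 2.6 subjects. The gain rows correspond to 1.5 and 3 subjects.

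**The case against.** The strongest reply has five parts.

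1. **The PR-then-PD case does not reach the primary endpoint, and Section 17.3.2.4 turns it into a tie.** Both statements are correct. The tie, however, comes from a section that contradicts Section 17.3.2.4.3 on whether SD needs confirmation, so the text still needs repair.

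2. **The loss of a PR–NE–PR response is a reading, not a rule.** This stands. A reader might infer that an incomplete middle scan costs a response while a skipped one does not. Section 17.3.2.4.2 gives both cases the same NE status, and nothing ranks NE below PR. Against that, Table 17.2 lists NE as an overall response, and Sections 11.4.1 and 17.3.2.4.4 give NE a response date, so counting it as a scan is not far-fetched. What remains is that the handling is undefined.

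3. **Evaluations within one time point share a single date (Sections 11.4.1 and 17.3.2.4.4), so two scans a few days apart may be one assessment.** This is fair for scans inside one window. It does not cover a scan between windows, such as day 55. Unscheduled scans are foreseen only for suspected progression, which limits how often such a scan would read PR.

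4. **The SAP may define the algorithm.** Section 11.7 leaves definitions and missing-data handling to it, and the text available here contains only the protocol, so this cannot be excluded. But the protocol sets the confirmation rule itself, and a different SAP rule would conflict with it.

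5. **A loose repair could inflate ORR.** If any second CR or PR at least 28 days later were enough, PR–SD–PR, or a PR read after PD, would count as confirmed. The repair must exclude both.

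**Conclusion.** The concern holds as a defect of definition. Within Section 17.3.2.4.3, PR then PD scores below SD then PD, with an effect on DCR only. Sections 17.3.2.4 and 17.3.2.4.3 conflict on whether SD must be confirmed. For the primary ORR, the missing minimum interval is a real but narrow gap, and the handling of an NE between two PRs is unspecified.

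Each affected subject moves the rate by 0.67 points, assuming all 150 planned subjects are in the Response Evaluable Set. A reader might infer that these sequences are common or that ORR is materially biased. The documents give no frequency for any of them, so neither inference is supported. The sensitivity figures show only what assumed rates would do, and the two ORR effects run in opposite directions. The point should be corrected before the responses are derived; it does not undermine the design or the sample size.

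**What to change.** Rewrite the rule in Section 17.3.2.4.3 to state that:

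- a CR or PR is confirmed when the next evaluable assessment at least 28 days after the first is also CR or PR and comes before any PD, with the lower of the two readings giving the class, as now;
- a reading less than 28 days after the first neither confirms nor breaks the response, unless it shows PD;
- an intervening NE or missed assessment is disregarded, but an SD at 28 days or later is not, so that a later CR or PR needs its own confirmation;
- an unconfirmed CR or PR seen at or after the minimum SD time (6 weeks, plus or minus 7 days) counts as SD.

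Amend Section 17.3.2.4 to require confirmation of CR or PR only, with SD governed by the minimum time.

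Under this text the protocol's own example remains SD. PR–PD and SD–PD both score SD at days 42 and 84. PR–NE–PR is a response. PR 42, PR 55, PD 84 is SD, and PR 42, PR 55, PR 84 is PR. PR–SD–PR is not a response, and neither is a PR read after PD. Because in-window scheduled scans are at least 28 days apart (day 49 to day 77), no in-window scheduled confirmation is lost.

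The cost is a small text change in the appendix, the SAP and the imaging charter, with no new data. A few early unscheduled confirmations would no longer count.
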